7.0 Study Timelines

7.1 Describe the duration of an individual subject's participation in the study.

Response:

The study is composed of five phases: medical history qualification (eight weeks), lead-in (four weeks), titration (six weeks), study period (12 weeks), and taper (two weeks).

7.2 Describe the duration anticipated to enroll all study subjects.

Response:

1-2 years

7.3 Describe the estimated date for the investigators to complete this study (complete primary analyses)

Response:

06/2016

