Those assigned to the lamotrigine treatment will take encapsulated lamotrigine daily for the duration of 20 weeks, consisting of a six-week titration, 12-week study period, and two-week taper. Possible doses for patients are 25mg BID, 50mg BID, 100 mg BID and 150mg BID during titration; 150mg BID or 100mg BID for the 12-week study period; 150mg QD or 100mg QD for Week 1 of the taper; and 75mg QD, or 50mg QD for Week 2 of the taper. Each increase in dose will be maintained for two weeks before deciding to further increase or decrease based on tolerability. Patients who discontinue at any point of the study will have a two-week taper consisting of the current dose QD for one week followed by half the dose QD for another week.

9.5 Describe the source records that will be used to collect data about subjects. (Attach all surveys, scripts, and data collection forms.)

Response:

- □ Ménière's Disease Patients-Oriented Severity Index (MDPOSI)
- □ Tinnitus Handicap Inventory (THI) questionnaire
- □ Clinical Global Impression-Severity & Change
- Dizziness Handicap Inventory (DHI) questionnaire
- □ AAO-HNS Ménière's disease self-assessment
- □ Patient Health Questionnaire-9 (PHQ-9)
- □ Generalized Anxiety Disorder 7-item scale (GAD-7)
- \Box Dosing Log
- □ Meniere's daily survey

9.6 What data will be collected including long-term follow-up.

Response:

Please see 9.5, plus:

 $\hfill\square$ Results of physical and neurological exams

- □ Audiogram
- \Box Drug dosing
- \Box CBC, CMP blood tests
- □ Lamotrigine blood levels (received from lab only after unblinding occurs)
- □ Urine pregnancy test results and creatinine levels
- \Box Drug adherence information
- □ Medications list
- □ Medical history
- 9.7 For HUD uses provide a description of the device, a summary of how you propose to use the device, including a description of any screening procedures, the HUD procedure, and any patient followup visits, tests or procedures.

Response: N/A

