12.0 Provisions to Monitor the Data and Ensure the Safety of Subjects

12.1 Describe the plan to periodically evaluate the data collected regarding both harms and benefits to determine whether subjects remain safe.

Response: Please also see section 12.7 pertaining to this question.

Adverse events (AE) will be reported to, evaluated and monitored by the PI, [name]. Any severe adverse event (SAE) will be reported to both the PI and the HSIRB within 24 hours of the research personnel becoming aware of the event. The PI will also evaluate and monitor any severe adverse event. In the event that 20% of the participants should experience an SAE the study will be terminated. In addition to terminating the study due to the previously specified criteria, at any point if the PI should decide to

terminate the study for other reasons, such as no clear evidence of benefit from the study or arising safety concerns, all participants will receive a phone call informing them of the new findings and they will be asked to come in for an early termination visit. Their safety will be assessed, the remaining drug will be collected, and new AEs or SAEs will be recorded. Each participant will also be informed that they will be reimbursed for travel for each visit that they had completed thus far. Reports of adverse events will be continually monitored by co-investigators in order to monitor subject response, ensure subject safety, and determine the necessity for an early termination.

After signing the informed consent, each participant will be assigned a participant number that will be used as coded identification for the entire study. The study's research personnel will compile and analyze incoming data, which will be reviewed on a bi-weekly basis to minimize the risks pertaining to the study. [name] will be responsible for data and safety oversight for the study. Data will be entered by the research personnel and verified at 100%. Data will be password protected, participant identity will be coded and access to identifying information will be limited to ensure confidentiality.

12.2 Describe what data are reviewed, including safety data, untoward events, and efficacy data.

Response: Please see 12.1. Also, the ratio of side effects vs. improvements in symptoms will be specifically evaluated.

12.3 Describe how the safety information will be collected (e.g., with case report forms, at study visits, by telephone calls with participants).

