Response: Safety information is collected at every visit; participants are asked about adverse events and complete questionnaires providing feedback on symptoms every visit throughout the duration of the study. Additionally, participants are encouraged to contact study personnel with any concerns, and are required to agree to report any degree of adverse health or psychological complaints regardless of whether or not they believe it is related to the study for the duration of the study including up to 28 days after their participation has concluded.

12.4 Describe the frequency of data collection, including when safety data collection starts.

Response: Data are collected at every visit; every 2 weeks for the first 10 weeks, then every 4 weeks from weeks 10 through 22, then two more visits separated by 1 week each. As previously stated, safety data are collected at every visit.

12.5 Describe who will review the data.

Response: Only the PI, Co-Investigator, Statistician, or Research Assistant at Dent Neurologic Institute will have access to the data and participant information. 12.6 Describe the frequency or periodicity of review of cumulative data.Response: Data will be reviewed bi-weekly.

12.7 Describe the statistical tests for analyzing the safety data to determine whether harm is occurring.

Response: I called IRB on 3/20/2015 to inquire about this and received verbal confirmation that the following procedures pertain to our study:

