This is a small (n=12), single location pilot study on the use of Lamotrigine to treat Meniere's disease. The study employs procedures that do not provide sufficient information to conduct statistical testing for potential harm. The main reason for this is because the way in which harm is determined is through probing participants about any side effects, adverse events, or complains at every study visit, as well as providing them with a means of contacting us M-F 8am-4:30pm if they experience any side effects between study visits. Additionally, the consent form outlines specific side effects to watch for that can be associated with the drug, including the course of medical action they should take if they develop the most common allergic reaction (rash). Finally, participants are explicitly asked at the time of consent whether or not they agree to report all adverse effects to the PI or research staff throughout the duration of the study, regardless of whether they believe it is related to the drug or not. All participants must agree to this in order to be in the study. While we have not encountered any adverse events or side effects, if we did, the PI would be informed and we would complete an adverse event report and submit to IRB immediately.

12.8 Describe any conditions that trigger an immediate suspension of the research.

Response: The research will be immediately suspended if the study drug is found to be unsafe due to a drug recall or similar event, or if the safety, security, or functionality of the facilities at which the study takes place become compromised in any way.

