13.0 Withdrawal of Subjects

13.1 Describe anticipated circumstances under which subjects will be withdrawn from the research without their consent.

Response: Participants may be withdrawn early without their consent if they develop a rash at any point during the study and [name] decides that it is caused by the treatment, if they develop a serious adverse event other than rash that requires discontinuing involvement in the study, if at any visit they are found to not be following dosing instructions.

13.2 Describe any procedures for orderly termination.

Response: For rash, participants are asked to immediately stop the medication, take an antihistamine, like Benadryl, return for an early termination visit and will be removed early from the study. If a different adverse event is experienced other than a rash, the participant will be asked to return for a visit (for which they are paid as per study compensation guidelines) and begin a two-week decrease of the current study drug dose. This decrease is the current study drug dose once a day for one week followed by half of the study drug dose once a week for another week. If a participant is found to not be following dosing instructions at any visit, [name] will review the situation and determine whether they need to be removed from the study, and if so, the participant will follow the same taper schedule and early termination visit required for those withdrawing due to adverse events other than rash.

13.3 Describe procedures that will be followed when subjects withdraw from the research, including partial withdrawal from procedures with continued data collection.

Response: Participants are informed in the consent form that if they choose to withdraw from the study, there will be no further information collected from them or about them. There isn't an instance of "partial withdrawal" in this study.

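### Section 13.3 stops all data collection when a participant chooses to withdraw, which conflicts with the adverse event reporting that 12.3 asks for up to 28 days after participation ends.

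*Combined protocol and SAP*

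**What the plan says.** **After voluntary withdrawal.** Section 13.3 gives the consent form's message as "if they choose to withdraw from the study, there will be no further information collected from them or about them". The template asks there about partial withdrawal with continued data collection, and the answer is that this study has none.

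**Adverse event reporting.** Section 12.3 says participants are "required to agree to report any degree of adverse health or psychological complaints", whether or not they think the study is the cause, "for the duration of the study including up to 28 days after their participation has concluded". It has no exception for withdrawal. Section 12.7 repeats the duty and adds "All participants must agree to this in order to be in the study". That restatement covers the study itself and does not mention the 28 days.

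**SAEs.** Section 12.1 says any SAE "will be reported to both the PI and the HSIRB within 24 hours of the research personnel becoming aware of the event". This too has no exception for withdrawal.

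**Drug after stopping.** Section 9.4 says: "Patients who discontinue at any point of the study will have a two-week taper". Section 7.1 lists the taper as one of the five study phases.

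**Exit visit.** Section 22.5, on payment to those who drop out, allows for an early termination visit but does not require one.

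**Removal by the investigator.** Sections 13.1 and 13.2 deal separately with participants taken out for rash, another adverse event or dosing non-compliance. The statement in 13.3 concerns only those who choose to leave.

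**The concern.** The two rules give opposite instructions for the same person over the same days. Suppose a participant withdraws by choice and telephones ten days later about a mild rash. Under 12.3 this is a report the participant agreed to make. Under 13.3 it is information from and about a withdrawn participant, which the study has said it will not collect. Staff who follow 13.3 would leave it unrecorded, and a participant who remembers the consent statement might not call.

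What is at stake is safety information. Section 12.7 explains that harm is detected by asking at visits and by participants getting in touch, and that no statistical test for harm is planned. After the last visit, participant reports are the only source. Rash matters for this drug: 14.1 lists it among the risks, and in the preliminary series in 2.2 four of 48 patients stopped because of side effects such as rash.

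**Working it through.** The point rests on comparing rules. The arithmetic only bounds its size.

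**1. The rules side by side, for a voluntary withdrawal taking effect on day D**

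| Event reported between D and D+28 | 12.3 | 13.3 | 12.1 | Result |
|---|---|---|---|---|
| SAE that staff learn of | asked for | not collected | must be reported | covered by 12.1 |
| Other adverse event | asked for | not collected | no 24-hour rule | conflict, unresolved |

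The second row is the finding. No other section says which rule governs.

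**2. Days per voluntary withdrawer**

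The limit in 12.3 is up to 28 days, so 28 is a maximum. Whether any of those days are on study drug depends on how 9.4 is read:
- If the taper applies to voluntary withdrawal and follows it, up to 2 × 7 = 14 of the 28 days are on study drug.
- If the taper still counts as participation (7.1), the 28 days start after it and 0 are on drug.

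The conflict exists under both readings.

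**3. Participants over the whole plan**

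Section 23.2 anticipates about 2 to 5 dropouts and does not say how many would be voluntary.
- None voluntary: 0 participant-days.
- All voluntary: 2 × 28 = 56 to 5 × 28 = 140 participant-days at most.

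**4. Participants still ahead at the 6/4/2015 update (11.2)**

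At that date 8 had completed and 2 had dropped out. Section 11.2 states the dropout rate as 25%, which is 2/8. Taken over all ten participants, 2/10 = 20%.
- With the requested total of 16: 16 − 10 = 6 at most still to finish; 6 × 0.20 = 1.2 to 6 × 0.25 = 1.5 expected dropouts.
- With the 12 still stated in 23.1: 12 − 10 = 2 at most; 2 × 0.20 = 0.4 to 2 × 0.25 = 0.5.

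So about one or two further dropouts at most would be expected, of whom none need be voluntary. Two would give 2 × 28 = 56 participant-days at most.

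**The case against.** **The specific rule governs the general one.** On this view 12.3 is an undertaking given at entry, 13.3 is the rule for those who leave, and a person who has left may still report by choice. This is a fair reading, but it does not settle what staff do with such a report. Once written down, it is information collected from the participant. If 13.3 is meant to govern, the 28 days in 12.3 do not hold for voluntary withdrawers and the text should say so. Either way an edit is needed.

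**The consent form may reconcile them.** It is not among the documents, so this cannot be excluded. The finding rests on what 13.3 says the form states.

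**The plan already softens the gap.** This stands in part. Section 12.1 covers any SAE that staff learn of, 22.5 allows for an exit visit, and the condition of entry in 12.7 does not extend to the 28 days. What remains is adverse events other than SAEs that are reported after withdrawal.

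**A stronger reading that does not hold.** A reader might infer that 13.3 undermines the stopping rule in 12.1: "In the event that 20% of the participants should experience an SAE the study will be terminated". At 12 participants, 2/12 = 16.7% and 3/12 = 25.0%; at 16, 3/16 = 18.8% and 4/16 = 25.0%. One missing SAE could therefore decide the matter at those counts. The documents do not support this as a consequence of 13.3:
- An SAE that staff learn of is reported under 12.1 whatever 13.3 says.
- An SAE that staff never hear of can be missed in a completer too. Reporting in 12.3 is left to the participant, and no contact is scheduled after participation for anyone. Rewording 13.3 adds none.
- Section 12.1 does not define the denominator of the 20%, so using 12 or 16 is an assumption.
- Section 12.7, in an answer that refers to an IRB call on 3/20/2015, says no adverse events had been encountered.

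**Conclusion.** The conflict is real and narrow. For participants who choose to withdraw, 13.3 bars recording of adverse events other than SAEs that 12.3 asks them to report, for up to 28 days each, and its message may discourage such reports. Depending on how the taper is read, up to 14 of those days or none are on study drug.

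The number affected is unknown and may be zero. If every anticipated dropout were voluntary, the total would be 56 to 140 participant-days at most. No planned test is affected and no effect on the stopping rule is claimed. Participants removed by the investigator fall outside the finding.

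The conclusion assumes that 13.3 describes the consent form correctly and that a report received after withdrawal counts as information collected. It should be corrected because the plan wants these reports and its own rule blocks recording them.

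**What to change.** Reword 13.3 and the matching consent statement along these lines:

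> If a participant chooses to withdraw, study procedures and efficacy data collection stop. Unless the participant refuses, adverse events reported up to 28 days after participation ends (12.3) are still recorded, and the participant is reminded of this at the early termination visit (22.5) if one takes place.

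This keeps withdrawal voluntary, since the participant can refuse. It adds no visit, scheduled contact or data system, so it will not bring to light an event that nobody reports. The cost is an IRB amendment for the protocol and the consent form, and re-consent of current participants as 28.2 requires when the form is revised.

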14.0 Risks to Subjects

14.1 List the reasonably foreseeable risks, discomforts, hazards, or inconveniences to the subjects related the subjects' participation in the research. Include as may be useful for the IRB's consideration, a description of the probability, magnitude, duration, and reversibility of the risks. Consider physical, psychological, social, legal, and economic risks.

There will be blood draws that are required for this study. Possible side effects from blood drawing include anxiety, faintness, vein inflammation, pain, bruising, or bleeding at the site of puncture. There is also a slight possibility of infection. Experienced medical personnel will be responsible for blood draws to minimize these risks.

There will be an electrocardiogram test. Skin irritation is rare but could occur during this test from the electrodes or gel that is used.

Participants may feel discomfort regarding questions asked in study questionnaires.

Participants will also be taking medications during the length of the study. All medications are FDA approved for use in patients. While lamotrigine is approved for use

in people who have a seizure disorder, the indication investigated during this study has not been approved.

Those assigned to the Lamotrigine treatment are at risk for rash, including Stevens-Johnson syndrome and toxic epidermal necrolysis, aseptic meningitis, hepatic and renal failure, DIC, arthritis, diplopia, sedation, dizziness, ataxia, headache, nausea and vomiting. Psychosis and depression are associated with epilepsy and occur in open label studies with all new AED's, but it is difficult to ascertain whether these relationships are causal. Incidence of rash was approximately 0.8% in adults receiving it as initial monotherapy for epilepsy and 0.08% in adults receiving it as initial monotherapy for bipolar and other mood disorders. This risk increases with concomitant valproate/divalproex use and reduces with slow titration. In order to prevent a rash, the daily dosage of lamotrigine will be slowly titrated by 50mg every two weeks. Valproate/divalproex, an anti-epileptic medication, is also prohibited from the study. If a study related rash does occur, the participant will be instructed to immediately discontinue the medication and to take an antihistamine drug. If the rash occurs with other serious symptoms associated with Stevens-Johnson syndrome and/or toxic epidermal necrolysis, such as fever, fatigue, sore throat, conjunctivitis or sores and/or ulcers in the mouth, lips or genital areas, participants are instructed to go to the emergency room. Hepatic and renal failure will be monitored with CBC and CMP blood analysis and a urine sample will be obtained for 24 hour creatinine clearance analysis as a screening, after titration and after the maintained dose period. Beginning with Visit 2, the C-SSRS will be conducted by a certified study staff to determine if there are any positive responses since last visit and whether it is safe for the participant to continue to participate in the trial. Any suicidal risk should be managed appropriately by the PI, who is a qualified mental health practitioner (MHP).

During the washout period and with placebo assignment, MD symptoms may become worse, stay the same, or improve. However, all participants are allowed to mitigate their symptoms with their choice of an abortive medication throughout the study. Common side effects from abortive medications include drowsiness, blurred vision, dry mouth, constipation or dizziness. Common serious side effects include an allergic reaction involving rash, difficulty breathing, and/or swelling of the face, lips, tongue or throat. Participants should read their specific abortive medication's package insert for a full list of side effects.

Hearing loss is another symptom of Ménière's disease currently without a treatment. During the study, participants' MD may worsen or stay the same and participants may experience fluctuating hearing loss or develop permanent hearing loss in the affected ear as a natural progression of the disorder.

All participants will be counseled on the definition of adverse events so that they may monitor for them. Additionally, participants will be asked for the presence of any adverse/serious events (specifically including those side effects associated with lamotrigine) at each visit. [name], as the PI, is directly responsible for assessing and monitoring all possible side effects and/or adverse events

Social risk is minimal; all measures will be taken to keep personal identifiable data confidential. Economical risk is small, but participants may have to take time off of work or find transportation in order to get to a required visit. Participants will be reimbursed for their travel up to 11 completed visits.

14.2 If applicable, indicate which procedures may have risks to the subjects that are currently unforeseeable.

N/A

14.3 If applicable, indicate which procedures may have risks to an embryo or fetus should the subject be or become pregnant.

Response: Lamotrigine is a Category C medication, meaning that animal reproduction studies have shown an adverse effect on the fetus and there are no adequate and well-controlled studies in humans. To avoid the potential risk to the fetus, pregnant and breastfeeding women are excluded from the study and all female participants must be willing to avoid pregnancy during the entirety of the study.

14.4 If applicable, describe risks to others who are not subjects.

Response: N/A

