Participants who are diagnosed with Ménière's disease, as determined by clinical history, ENT confirmation and an audiogram, will qualify if they also have had two or more Ménière's vertigo attacks in a four-week span for two consecutive four-week periods (the qualification period). Those who meet these criteria will then need two or more Ménière's vertigo attacks during a four-week lead-in period to further establish a baseline and verify randomization eligibility. Participants are allowed from the beginning of the lead-in to take their choice of a symptomatic abortive medication according to its package instructions for Ménière's vertigo attacks that last longer than 30 minutes with nausea and/or vomiting. Symptomatic abortive medications include, but are not limited to, meclizine (Antivert), Valium, diazepam, or Zofran. The abortive medication can be used throughout the study regardless of treatment assignment and its use will be recorded. Twelve eligible participants, with a minimum total of six attacks during the qualification and lead-in periods, will be randomly assigned to either a placebo or lamotrigine treatment group. Randomization will be conducted by UBSoPPS Research Pharmacy. The study drug and matching placebo will be titrated from 25mg twice a day (BID) up to 150mg BID over a six week period. During titration, clinic visits are scheduled every two weeks to assess any adverse events, symptoms, quality of life, and compliance. Those who cannot tolerate the 150mg BID dose may return to a 100mg BID dose during an unplanned visit. However, if a participant is unable to tolerate the 100mg BID dose they will be withdrawn from the study. Participants will maintain the 150mg BID or 100mg BID dose for a 12-week period with clinic visits every four weeks to assess their progress. Between all study visits, participants are asked to complete a daily survey describing their symptoms. This survey is hosted by polleverywhere.com and can be completed through text message, an online website, or with a paper document- whatever method is preferred by the participant. At the conclusion of the 12-week study period, a study staff will be un-blinded

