At Visit 2, after the four week lead-in, inclusion/exclusion criteria will be re-evaluated. This includes a review of any concomitant medications. Participants will be asked to hand in their Ménière's survey if they opted for the paper document. The surveys will be reviewed to ensure that abortive measures were only used during the severe attacks, as instructed. The Principal Investigator will assess any possible adverse events and then staff will administer the questionnaire batch. If the participant is eligible for randomization, he/she will be assigned to either a placebo or lamotrigine treatment group. Assignment will be based on a randomization conducted by UBSoPPS Research pharmacists, and the participant will be considered "enrolled" in the study at this point, and from this point on, all medical services, except abortive medication(s) of the patient's choice) are study-related and are not billed to the patient's insurance. Both groups will receive an amber vial of 28 pills with instructions to take one pill twice a day. Those in the lamotrigine group will be taking 25mg BID while those in the placebo group will be taking encapsulated microcrystalline cellulose. A drug dosage log will also be given to participants and they will be asked to write down the number of pills taken. Participants will be advised to notify the Principal Investigator or study staff if they develop rashes or other side effects. If the principal investigator decides that the rash is medication related, the participant will immediately stop the medication, return for an early termination visit and be terminated early from the study. Serious adverse events requiring withdrawal and unrelated to rash will return for an early termination visit and begin a two-week taper. If at any visit a participant is found to be non-compliant with dosing instructions, the Principal Investigator will assess the situation and determine if early termination is required. If the participant is terminated, they will follow the same taper schedule and early termination visit required for those withdrawing due to adverse events other than rash. Staff members will also remind participants to complete the daily survey and how to do so.

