Two weeks later at Visit 3, current medications and adverse events will be reviewed by the Principal Investigator. A staff member will collect the medication containers, conduct a pill count and collect and review the dosage log and daily Ménière's survey responses. If the participant is determined to be compliant the staff member will administer the questionnaire batch. Continuing participants will receive an amber vial of 28 pills with instructions to take one pill twice a day. The medication will either be lamotrigine 50mg BID or the matching placebo. Staff members will then hand out another dosage log and remind participants to complete the daily survey. Participants are asked to return in two weeks.

At Visit 4, current medications and adverse events will be reviewed by the Principal Investigator. A staff member will collect the medication containers, conduct a pill count and collect and review the dosage log and daily Ménière's survey responses. If the participant is determined to be compliant the staff member will administer the questionnaire batch. Continuing participants will receive an amber vial of 28 pills with instructions to take one pill twice a day. The medication will either be lamotrigine 100mg BID or the matching placebo. Staff members will then hand out another dosage log and remind participants to complete the daily survey. Participants are asked to return in two weeks.

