At Visit 5, current medications and adverse events will be reviewed by the Principal Investigator. Participants will complete another physical and neurological exam, a comprehensive audiogram with tympanometry, and a urine pregnancy test for females of reproductive age (<50yrs). Blood will be drawn, centrifuged and shipped to Kaleida Health's labs to analyze study drug levels. Additionally, a urine sample will be obtained for 24 hour creatinine clearance analysis as a screening measure for healthy kidney and liver function, to verify participants' ability to continue in the study. Study drug level results will be separated from other testing results and sent to UBSoPP Research Pharmacy to hold until the blind is broken and compliance can be reviewed. A staff member will collect the medication containers, conduct a pill count and collect and review the dosage log and daily Ménière's survey responses. If the participant is determined to be compliant, the staff member will administer the questionnaire batch. Continuing participants will receive an amber vial of 56 pills with instructions to take one pill twice a day. Participants' clinical response and tolerability will be assessed and if a participant reports no serious side effects from medications, the study drug will be further titrated to 150 mg BID or the matching placebo. If the participant finds that they cannot tolerate the 150mg BID dose, they are able to come into the clinic for an unscheduled visit and decrease to 100mg BID. Staff members will then hand out another dosage log and remind participants to complete the daily survey. Participants are asked to return in four weeks.

At Visit 6, current medications and adverse events will be reviewed by the Principal Investigator. A staff member will collect medication containers, conduct a pill count and collect and review the dosage log and daily Ménière's survey responses. If the participant is determined to be compliant the staff member will administer the questionnaire batch. Continuing participants will receive an amber vial of 56 pills of the same dosage, either 150mg BID or 100mg BID, with instructions to take one pill twice a day. Staff members will then hand out another dosage log and remind participants to complete the daily survey. Participants are asked to return in four weeks.

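### The 50 mg two-weekly increase that section 14.1 gives as a rash safeguard does not match the titration schedule, and sections disagree on the week-2 taper frequency

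*Combined protocol and SAP*

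**What the plan says.** **Titration.** Section 14.1 discusses rash, including its most serious forms, and says "This risk increases with concomitant valproate/divalproex use and reduces with slow titration". It then gives the measure taken in this trial: "In order to prevent a rash, the daily dosage of lamotrigine will be slowly titrated by 50mg every two weeks".

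The dosing sections describe the titration as follows.

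- Section 9.1: "titrated from 25mg twice a day (BID) up to 150mg BID over a six week period".
- Section 9.2, Visit 2: "Those in the lamotrigine group will be taking 25mg BID".
- Section 9.2, Visit 3, two weeks later: "The medication will either be lamotrigine 50mg BID or the matching placebo".
- Section 9.2, Visit 4, after two more weeks: "The medication will either be lamotrigine 100mg BID or the matching placebo".
- Section 9.2, Visit 5, after two more weeks and subject to tolerability: "the study drug will be further titrated to 150 mg BID or the matching placebo".
- Section 9.4, repeated in section 30.1: "Possible doses for patients are 25mg BID, 50mg BID, 100 mg BID and 150mg BID during titration". Both sections add that each increase is held for two weeks.

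**Taper.** Section 13.2 covers participants removed early for an adverse event other than rash or for not following dosing instructions. It sets a two-week reduction: the current dose once a day for a week, then half the dose once a week for the second week. Sections 9.4 and 30.1 give half the dose QD in the second week for patients who stop at any point. Section 9.2 also gives QD at Visit 8, but for participants who have finished the 12-week period.

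**The concern.** Section 14.1 links rash risk to the speed of titration and then states a speed. That statement is part of the risk description on which the IRB relies. If the schedule rises faster than the text says, the board has been given a mitigation that the dosing sections do not deliver. Rash is the first drug risk listed. In the preliminary series in section 2.2, four of 48 patients (4/48 = 8.3%) stopped because of side effects such as rash.

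The taper conflict concerns conduct. A participant who leaves early for an adverse event other than rash falls under both 13.2 and 9.4/30.1, and the two give different instructions for the second week.

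**Working it through.** No power or alpha calculation is involved. The check converts each dispensed dose to a daily dose, takes differences between visits, and compares them with the increment stated in 14.1.

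Daily dose = 2 × BID dose. The doses come from section 9.2, and the four levels are confirmed in 9.4 and 30.1. The last column applies the 14.1 rule from the same start: 50 + 50 × (weeks ÷ 2).

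| Visit | Weeks on drug | BID dose (mg) | Daily dose in schedule (mg) | Step (mg/day) | Daily dose under 14.1 rule (mg) |
|---|---|---|---|---|---|
| 2 | 0 | 25 | 50 | – | 50 |
| 3 | 2 | 50 | 100 | +50 | 100 |
| 4 | 4 | 100 | 200 | +100 | 150 |
| 5 | 6 | 150 | 300 | +100 | 200 |

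The stated 50 mg increment is reproduced only at the first step.

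- Planned rise: 300 − 50 = 250 mg/day over three steps, an average of 250/3 = 83.3 mg per step.
- Three steps of 50 mg add 150 mg, which is 100 mg short of that rise.
- At 50 mg every two weeks, the 250 mg rise needs 250/50 = 5 steps, or 10 weeks. Section 9.1 gives six weeks.

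Three readings that might rescue the sentence were tried.

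1. Per single dose instead of per day: the steps are +25, +50 and +50. They are still not uniform, and the sentence refers to daily dosage.
2. Counting the start as a step from zero: the steps are +50, +50, +100 and +100. Four steps of 50 mg reach 200 mg/day, not 300.
3. Treating 150 mg BID as optional: the Visit 4 step from 50 to 100 mg BID is already +100 mg/day, so the conflict remains for a participant who never reaches the top level.

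For the taper, the administrations in week 2 are:

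| Starting dose | Half dose (mg) | QD, sections 9.4 and 30.1 | Once a week, section 13.2 |
|---|---|---|---|
| 150 mg BID | 75 | 7 × 75 = 525 mg | 1 × 75 = 75 mg |
| 100 mg BID | 50 | 7 × 50 = 350 mg | 1 × 50 = 50 mg |

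Read literally, this is seven doses against one.

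**The case against.** The strongest reply on titration is that staff do not face two competing schedules. The visit instructions in 9.2 and the drug descriptions in 9.4 and 30.1 agree with one another, and the only different statement is in the risk narrative. Dosing may therefore have been uniform in practice. Nor is the 50 mg step the only protection. Section 14.1 also prohibits valproate/divalproex, requires the drug to be stopped for a study-related rash, and sends participants with serious accompanying symptoms to the emergency room. Adverse events are reviewed at every titration visit, and the move to 150 mg BID depends on tolerability. Section 12.7 reports no adverse events at the time of writing.

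All of this stands, and it limits the point. The defect is a mismatch between a stated safeguard and the planned schedule; there is no evidence here of harm or of inconsistent dosing. The mismatch itself remains, because the other protections do not make the stated rate agree with the schedule.

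On the taper, the reply is that once a week is probably a slip, since every other taper description says QD. That is plausible, and the seven-to-one ratio depends on a literal reading. The wording nevertheless sits in the section that governs early termination, so it needs correction or confirmation. Taken alone it would be a small wording item; the titration mismatch carries the weight.

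**Conclusion.** The point holds on both parts. Two of the three planned increases are 100 mg/day against a stated 50 mg/day, and at week 6 the schedule stands at 300 mg/day against 200 mg/day under the 14.1 rule. The week-6 comparison assumes full escalation to 150 mg BID; the Visit 4 conflict does not need that assumption. The second taper week differs between 13.2 and 9.4/30.1 for the same participants, by one dose against seven if read literally.

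The primary endpoint, sample size, power and analysis do not depend on either part. This should be fixed because a stated safety measure and a withdrawal rule are each contradicted elsewhere in the same document. Which titration or taper is right is a clinical matter and is not judged here.

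**What to change.** The clinical team should reconcile the passages in one amendment, so that:

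- sections 9.1, 9.2, 9.4, 14.1 and 30.1 carry one consistent titration statement; and
- sections 9.2, 9.4, 13.2 and 30.1 carry one week-2 taper frequency.

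The consent form was not in the text reviewed and should be checked against the reconciled wording. If it has to be revised, section 28.2 requires participants still in the study to be consented again.

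The cost is a wording amendment, a consent-form check, a notice to staff and pharmacy, and possibly re-consent of a few people. The 6/4/2015 update in section 11.2 asks to raise enrolment to 16, so the correction could reach later participants. For the 8 who had completed by then it is retrospective. The same update reports 2 dropouts without giving reasons, so whether the 13.2 taper applied to either of them should be checked in the study records.
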